4.4.2 Group Cii- Long term evaluation group

- 1-5. As described above for all groups
- 6. Complete clinical evaluation session (tables 5, 7, 8, 10, 11, 12, 14) (M31)
- 7. First FrailSafe system home visit (M31):
 - Blood sampling for telomeres
 - Fill in the evaluation form regarding the participant's housing (table 18)
 - Collect any questionnaires filled in by the participant since the last visit: written texts, social media and big five questionnaires
 - Complete any missing information of the clinical evaluation (i.e. scanning of a forgotten prescription, scanning of an older written text provided by the participant, write down dictated text)

- Installation of the currently available FrailSafe system and explication of the use, the purposes and the technical issues of the FrailSafe material (Session 3.8). Verification of its correct function
- Provide contact details and instructions in case of any help needed
- Set the next appointment to retrieve the FrailSafe material (5th day)
- 8. Maintenance of the FrailSafe system at home during 60 days
- 9. Short satisfaction interview in the day of FrailSafe system retrieval
- 10. One follow-up telephone call (M34)(table 17)
- 11. [Only for Patras]: Second blood sampling (M35)
- 12. Last clinical evaluation (M36) (tables 5-14)
- 13. Data collection of written text after the first time (table 16) (M36). The participant will either be helped to provide text by dictation or (s)he will write it down during the clinical assessment appointment.
- 14. Study's completion verification (table 20). Normally at the end (M36), but could be in anytime in case of premature withdrawal.

4.5 Group D- Control

- 1-5. As described above for all groups
- 6. Complete clinical evaluation session (tables 5, 7, 8, 10, 11, 12, 14) (M31)
- 7. Blood sampling for telomeres (M31)
- 8. One follow-up telephone call (M33)(table 17)
- 9. Last clinical evaluation (M36) (tables 5-14)
- 10. Data collection of written text after the first time (table 16) (M36). The participant will either be helped to provide text by dictation or (s)he will write it down during the clinical assessment appointment.
- 11. Study's completion verification (table 20). Normally at the end (M36), but could be in anytime in case of premature withdrawal.

5. Architecture of data analysis

5.1 Definition of Frailty Indices

In order to render clinical results measurable, there is a need to define loss of reserve, independently of frailty status as this is defined by Fried's criteria.

On the other hand, FrailSafe Database contains variables at different time points from

- Clinical Evaluation
- Follow up assessment

• FrailSafe system metrics

In this scope, a new combined index (**Combined Frailty index: CoFI**), that will express frailty status relevant to the study's measurements, will be created by adding up two other frailty indices derived from the study, the **Clinical Frailty Index (CIFI**), corresponding to the results of the clinical evaluation, and the **Technical Frailty Index (TFI**), corresponding to the metrics derived from the FrailSafe system devices.

Table 21. Frailty Indices definition

CIFI (Clinical Frailty Index): score corresponding to the findings of the clinical evaluation in a time-spot (Appendix I)
TFI (Technical Frailty Index): accumulated score derived from the FrailSafe system
metrics during certain time intervals of observation (Appendix II)
Co FI (Combined Frailty index): combined Clinical and Technical frailty score

Each time a programmed clinical evaluation is effectuated, a CIFI score will be calculated, which will be composed by several items that correspond to various aspects of frailty, as they are described by the clinical evaluation sub-questionnaires

[figure not shown]

Figure 6. Example of Frailty Indices for a subject belonging to group A.

Similarly, a TFI will be calculated for each FrailSafe system installation, practically, for each FrailSafe home visit. For example, for group A, there will be 2 TFIs calculated, TFIA1 and TFIA2. Similarly for group B there will be 7 TFIs calculated.

Finally, for example for group A, a combined FI, by adding up CIFI and TFI will be calculated twice: CoFIA1=CIFIA1+TFIA1 and CoFIA2=CIFIA2+TFIA2.

5.2 Definition of outcomes

5.2.1 Hard Outcomes

Hard outcome events can be described as significant crude life events that result, because of loss of physiological reserve, in stressful conditions.

Seven main clinical outcomes are defined as hard:

- Fall
- Fracture
- Hospitalisation (non programmed)
- Institutionalisation
- Death
- Decline in ADL or IADL capacity (significant change is defined as decline in at least 1 point in the ADL score and/or 1 point in IADL score)

5.2.2 Proxy outcomes

Due to the limited number of participants, the tight timeframe of the project and the frequency of occurrence of Hard Outcomes, we propose the use of proxy outcomes that we are confident that we will be able to measure and to use in the data analysis part of the project to draw some solid conclusions. The proxy outcomes could also be considered as a diagnostic, early detection tool of a declining condition that may lead to a hard outcome. By keeping a concise, short, practical yet informative track of the change in proxy outcomes we will be able via coaching and interventions to postpone the inevitable occurrence of a Hard outcome, thus improving prognosis and quality of life.

Repeated clinical evaluations are carried out in the following domains: physical, cognitive, psychological, nutritional, and wellness. Loss of function in each domain can indirectly describe loss of physiological reserve, which underscores frailty, and consequently the adverse events of frailty (described above in 5.2.1). The clinical experts of this consortium in a consensus meeting have agreed on a key clinical assessment of each domain, which best describes loss of reserve and is believed to predict adverse outcome.

Therefore, as proxy outcomes have been selected the following:

- Gait speed (Physical Domain)
- MoCA and/or MMSE (Cognitive Domain)
- GDS (Psychological Domain)
- Weight loss (Nutritional Domain)
- Health status self-assessment (General health/Wellness Domain)

The clinicians in the process of selecting a proxy outcome in each domain made use of the bibliography and their expert opinion. At the end of the clinical studies, analysis will be carried out correlating these proxy outcomes to the hard outcomes observed in participants and, if possible, explore validity and reliability.

Review of the bibliography showed that gait speed test has been established as the test with the strongest correlation to frailty (72), and has been linked with the hard outcomes, such as falls and mortality (73,74). Reduced MoCA and MMSE scores, though the later to a lesser extent as less sensitive to the detection of mild cognitive decline, have been linked both with

frailty and adverse outcomes in certain elderly populations (75,76). GDS has been correlated with frailty and may predispose to falls, hospitalization, and increased mortality (77-79). Unintentional weight loss (i.e., more than a 5% reduction in body weight within six to 12 months) is associated with increased morbidity and mortality and may lead to decline of ADL, falls and hip fractures in women (80-82). Self-assessment of health status appears to be a good measure of physical health and risk of death (83,84).

Changes of the measurements of the proxy outcomes will be assessed at regular intervals and at the entry and end of the study interval (according to the study protocol).

The choice of the proxy outcomes has been based on clinical evidence from literature review and clinical practice as described previously. Their contribution and necessity in the Frailsafe project, as well as the mathematical procedures to be applied are described in more details next.

The idea of continuous monitoring with the Frailsafe devices is based on the observation that the physiological decline varies across individuals and that the critical time point to act (e.g. to provide treatment to the older person) follows his/her personalized curve of decline (as shown with red and cyan arrows in the figure below) and does not only depend on the physiological condition at the first evaluation.

[figure not shown]

Figure 7. Change of proxy variable f_i over time (measured at 4 time points) for two subjects shown in red and cyan, respectively. The two curves are fitted to the measurements.

Our assumption is that the proxy variables are the main predictors of the hard outcomes but just one time instance is not enough, whereas 1) predicting their values in future instances might help to better estimate adverse events and 2) the incorporation of the variables from the Frailsafe devices might provide additional knowledge that might help to differentiate future states. Therefore the proxy variables will act as the backbone in our predictions, whereas the FS variables will be selected according to their predictive ability and significance.

The first step in our methodology will be to model the temporal change of the proxy variables. We will investigate simple models to represent the temporal variation of the data, such as the quadratic polynomial, for each one of the N proxy variables:

$$f_i(t) = a - b * t - c * t^2$$
, $i=1,..., N$

where a, b and c positive parameters that indicate the starting point and the rate of linear and more rapid (quadratic) change, respectively. Zero values of b and c model the steady state. If less than three time points are available, the estimation of c is not possible and thus will be taken as zero. After completing three clinical evaluations, c can be also estimated.

The second step in the methodology will be to identify the important FS variables as the ones which correlate well with any of the estimated proxy variables f_i . Since an event can have a delayed effect, lag correlations will be also examined to identify possible latencies. If such correlations prove to exist, we will have the means to predict future responses using the FS devices.

Furthermore, in the last step of our methodology when more data become available, statistical (survival) analysis will be performed, using for example the Cox proportional hazards model, in order to find frailty indexes that predict the hard outcomes. This step will have more statistical power when a adequate number of hard outcomes will have happened, thus it will be applied after the 2nd clinical evaluation of group A, as well as by the end of the project. More details on the proposed scores (technical and medical) are provided in Section 5.1 and Appendices I and II.

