2.2 Participants' characteristics

The Clinical study will be performed in 3 Clinical Centers: University of Patras (UoP), Greece; INSERM-Nancy, France; and MATERIA- Nicosia, Cyprus. Each Center will recruit 170 individuals for the FrailSafe study. By this way a total of 510 community living subjects aged 70 years and older will be recruited. The inclusion and non-inclusion criteria are demonstrated in table 1.

Table 1. Inclusion and exclusion criteria

Inclusion criteria
Age ≥70 years
Informed consent provided
Exclusion criteria
Lack of wish to participate
Consent withheld
Inability to give consent because of incapacity
Inability to walk
Inability to speak Greek or French (see clinical centers)
Diagnosis of clinically significant cognitive impairment or score less than 24 on the Mini– Mental State Examination
Diagnosis of advanced malignancy, other terminal illness or an estimated life expectancy of less than 12 months
Active psychiatric disorder based on medical records or clinical opinion at the time of recruitment, current substance users, or excessive alcohol drinkers.

The numerical threshold for "older age" has always been controversial, though most widely accepted was the age of 65 years, corresponding in the usual age of retirement. Still, nowadays "young old" individuals maintain a good general health condition and with the exception of special cases, frailty is most likely to be encountered in older age ranges. In the FrailSafe study, since we need to include people in non-frail, pre-frail, as well as frail conditions, it was decided that the age threshold will be that of 70 years.

In order to be able to comply better with the requirements of the study (usage of technical material, cooperation for the testing of novel equipment, need for participant's feedback and relatively long follow up period), subjects with highly debilitating conditions, such as inability to walk, presence of clinically significant cognitive impairment, or active psychiatric

disorder will be excluded from the study. Similarly, subjects with serious medical conditions that convey a guarded prognosis (estimated life expectancy of less than 12 months) will be excluded as well.

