2.3 Groups

All participants will be given a unique number by the time they are allocated in four groups (table 2), with the addition of the code number of each centre in front: (1 for Patras, 2 for Cyprus and 3 for Nancy). For each centre, participants with numbers 001 to 080 will belong to the Start Up Group (A), the 40 following will belong to the Main Group (B), the 25 following afterwards will belong to the Evaluation Group (C) and the last 25 to the Control Group (D). The Evaluation Group (C) will be further divided in two parts: participants with numbers 121-140 will belong to the "standard" Evaluation Group; while those with numbers 141-145 will belong to the Long Term Evaluation Group, with an augmented intensity of following up.

Group	Serial Number
A- Start Up	001-080
B- Main	081-120
C- Evaluation	121-145
Ci- Standard Evaluation	121-140
Cii- Long term Evaluation	141-145
D- Control	146-170
With the prefix of the centre number	1 for Patras, Greece
	2 for Nicosia, Cyprus
	3 for Nancy, France

Table 2. Participants' ID numbers

In case of exclusion or premature withdrawal of a participant, (s)he has been replaced by a new subject, to whom a new unique ID number has been given. The substitute subjects were given the number of the individual they have replaced with the addition of 500. For example, if the participant number 1094 withdrew from the study (subject number 94 from the first recruitment centre), the subject that replaced him/her will take the number 1594

(=1094+500). For subject number 3164 who withdrew (participant number 164 from the third recruitment centre), the subject replacing him/her will take the number 3664 (=3164+500). However, participants' replacements took place only until M19. Any subject that dropped off after July 2017, has not been and will not be replaced due to lack of time for catching up with the minimum follow up time period required (M19 represents the middle timeline of the project).

The number of the participants allocated in each group is already agreed in the original proposal and corresponds mostly to issues of availability of material and workforce in the context of actual financial potential and less to pure mathematical calculations, due to the originality of the project and the absence of a previous reference to consider for sample size calculations.

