4.1 All groups

- 1. Quick first verification of inclusion and exclusion criteria
- 2. Randomization to groups (only applicable for group C and D)
- 3. Informed consent and attribution of a unique ID number
- 4. First part of clinical evaluation session: questionnaires to verify inclusion and not inclusion criteria, Fried's criteria of frailty, medical history and cognitive assessment will be administered (tables 4, 5, 6, 9, 13).
- 5. Second verification of the inclusion/exclusion criteria according to the first part of the clinical evaluation's results. If exclusion, replacement of the participant and repetition of steps 1-5 for the next candidate

The steps from this point down and their time programming will differ according to group allocation.

4.2 Group A- Start Up group:

- 1-5. As described above for all groups
- 6. Complete clinical evaluation session (tables 7, 8, 10, 11, 12, 14) (M≥6)
- 7. Data collection regarding social interaction and natural language analysis:
 - Data collection of written text for the first time (table 15), where the participant will either be helped to provide text by dictation or be asked to prepare it him/herself in his/her home and deliver it to us in the next appointment and
 - self-administered questionnaires The Social Media (annex 16) and the Big five (annex 17) questionnaire will be given to participants in order to fill them in themselves and deliver them to us in the next appointment
- 8. First FrailSafe system home visit (M≥6):
 - Blood sampling for telomeres
 - Fill in the evaluation form regarding the participant's housing (table 18)
 - Collect any questionnaires filled in by the participant since the last visit: written texts, social media and big five questionnaires
 - Complete any missing information of the clinical evaluation (i.e. scanning of a forgotten prescription, scanning of an older written text provided by the participant, write down dictated text)
 - Installation of the currently available FrailSafe system and explication of the use, the purposes and the technical issues of the FrailSafe material. Verification of its correct function
 - Provide contact details and instructions in case of any help needed
 - Set the next appointment to retrieve the FrailSafe material (5th day)
- 9. Maintenance of the FrailSafe system at home during 3-5 days

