- 10. Daily phone calls during the instauration of the FrailSafe system to catch up with the experience of the use of the material and any problems that may have arisen
- 11. Short satisfaction interview in the day of FrailSafe system retrieval
- 12. Telephone Follow-up after the retrieval of the FrailSafe in a 3 months' basis (table 17). (M9-M24)
- 13. Second clinical evaluation (M27) (tables 5-14)
- 14. Data collection of written text after the first time (table 16) (M27). The participant will either be helped to provide text by dictation or be asked to prepare it him/herself in his/her home and deliver it to us in the next appointment
- 15. Second FrailSafe system instauration (M27)
 - [Only for Patras]: blood sampling
 - Fill in the evaluation form regarding the participant's housing (table 18)
 - Collect any questionnaires filled in by the participant since the last visit (written texts)

- Complete any missing information of the clinical evaluation (i.e. scanning of a forgotten prescription, scanning of an older written text provided by the participant, write down dictated text)
- Administration of follow up questionnaire (table 17)
- Installation of the currently available FrailSafe system and reminding of the use, the purposes and the technical issues of the FrailSafe material (Session 3.8). Verification of its correct function
- Provide contact details and instructions in case of any help needed
- Set the next appointment to retrieve the FrailSafe material (5th day)
- 16. Maintenance of the FrailSafe system at home during 3-5 days
- 17. Daily phone calls during the instauration of the FrailSafe system to catch up with the experience of the use of the material
- 18. Telephone Follow-up after the second retrieval of the FrailSafe (M30) (table 17)
- 19. Last clinical evaluation (M33) (tables 5-14)
- 20. Data collection of written text after the first time (table 16) (M33). The participant will either be helped to provide text by dictation or (s)he will write it down during the clinical assessment appointment
- 21. Last telephone follow up M36
- 22. Study's completion verification (table 20). Normally at the end (M36), but could be in anytime in case of premature withdrawal.

Did the patient complete the study as predicted?	1. Yes 2. No

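### The end-of-study correlation of proxy outcomes with hard outcomes does not require the proxy change to precede the event, though roughly half or more of scheduled follow-up comes before any measured change

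*Protocol*

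**What the plan says.** Section 5.2.2 names gait speed, MoCA and/or MMSE, GDS, weight loss and self-assessed health as proxy outcomes. It says that tracking their change should allow action before a hard outcome occurs. It then states: "Our assumption is that the proxy variables are the main predictors of the hard outcomes but just one time instance is not enough". The first modelling step fits a time curve to each proxy, with a starting value, a linear term and a quadratic term. The proxies are to be checked at the end of the clinical studies: "analysis will be carried out correlating these proxy outcomes to the hard outcomes observed in participants".

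The dates of the second clinical evaluation are in Section 4. Group A starts with "Complete clinical evaluation session (tables 7, 8, 10, 11, 12, 14) (M≥6" and continues with "Second clinical evaluation (M27) (tables 5-14" (both in the Section 4.2 list), although Section 2.5 gives M26 for the second evaluation. Group B is evaluated at M10 and M16 (Section 4.3). Groups C and D are evaluated at M31 and again only at study end; for D the entry is "Last clinical evaluation (M36) (tables 5-14".

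**The concern.** A slope cannot be estimated from one measurement. For any hard outcome before the second evaluation, the measured change is completed after the event. A fracture or an unplanned hospital stay can itself slow gait, reduce weight or raise GDS. Section 3.1.3 says that fractures impair functional status. If all observed events enter one correlation, such decline looks like successful prediction. A participant who dies before the second evaluation has no measured change at all.

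The stake is wide. Section 5.2.2 makes the proxies the core of the prediction models, and objectives MO1 to MO6 in Table 24 all refer to proxy and hard outcomes.

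Nothing else in the protocol sets the order. The lag correlations in Section 5.2.2 link device variables to proxies, not proxies to hard outcomes. The survival step, with the Cox model as an example, is for frailty indexes. Section 5.4.1 plans imputation, which gives no time order.

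**Working it through.** The protocol gives no figure for this, so there is nothing of its own to reproduce. The share of follow-up before a measured change is built from the schedule.

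**Group sizes.** "Each Center will recruit 170 individuals for the FrailSafe study", so 3 × 170 = 510. Per centre, "participants with numbers 001 to 080 will belong to the Start Up Group (A), the 40 following will belong to the Main Group (B") and "the 25 following afterwards will belong to the Evaluation Group (C) and the last 25 to the Control Group (D"). Hence A = 240, B = 120, C = 75, D = 75.

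**Formula.** Share = Σ n × (second evaluation − first evaluation) ÷ Σ n × (M36 − first evaluation), with no dropout.

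| Group | Before second evaluation | All follow-up | Share |
|---|---|---|---|
| A (M6, M27) | 240 × 21 = 5,040 | 240 × 30 = 7,200 | 70% |
| B (M10, M16) | 120 × 6 = 720 | 120 × 26 = 3,120 | 23% |
| C and D (M31, M36) | 150 × 5 = 750 | 150 × 5 = 750 | 100% |
| Total | 6,510 | 11,070 | 58.8% |

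**Variants.**
- Group A second evaluation at M26: 6,510 − 240 = 6,270; 6,270 ÷ 11,070 = 56.6%.
- All of group A entering at M10 (the text allows M6 or later): 5,550 ÷ 10,110 = 54.9% (M27) or 5,310 ÷ 10,110 = 52.5% (M26).
- Monitoring from the first triplet (Section 3.3), using the mitigated sessions of Section 2.6. Group A starts at M11 (27 × 3 = 81), M14 (25 × 3 = 75) and M17 (28 × 3 = 84); B starts at M12. Before: 81×16 + 75×13 + 84×10 + 120×4 + 750 = 4,341. All: 81×25 + 75×22 + 84×19 + 120×24 + 750 = 8,901. Share 48.8%, or 4,101 ÷ 8,901 = 46.1% with M26. Starting B at M13 lowers each by less than one point.

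Follow-up left after a measured change is 11,070 − 6,510 = 4,560 person-months (41%), or 4,800 (43%) with M26. None of it is in C or D.

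**Illustrative simulation, group A.** Setting: n = 240, entry M6, change measured at M27, follow-up to M36, true predictive value zero, change SD 0.12 m/s, all events survivable. Event rate, gait loss and the share of events that leave a lasting loss are assumptions; the protocol gives none of them.

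| Event rate per year | Lasting loss (m/s) | Share of events with lasting loss | Mean r | p<0.05 |
|---|---|---|---|---|
| 25% | 0.06 | 100% | −0.18 to −0.19 | 82 to 84% |
| 10% | 0.06 | 100% | −0.15 | 64% |
| 25% | 0.03 | 100% | −0.09 | 31% |
| 25% | 0.06 | 50% | −0.09 | 29% |
| 25% | 0.06 | 25% | −0.05 | 12% |
| 10% | 0.03 | 25% | −0.02 | 7% |

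The first row spans repeated runs of the same setting. When the same change is related only to events after M27, the mean correlation is about 0 and p<0.05 occurs in about 5% of runs in every row.

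**The case against.** The strongest reply is that this is an omission. The sentence on the correlation does not itself say change, and time ordering is often left to an SAP, which is not shown here. That has some force, and it rules out saying that the analysis will certainly go wrong. It does not remove the point. The protocol already fixes when the correlation is done and which events it takes in, and the surrounding text makes the trajectory the predictor.

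Four further points limit the size:
- Entry values exist for everyone. Two items recall change over the past year already at entry: weight loss (Table 9) and health compared with a year ago (Table 14). A reader might infer that no proxy change can be scored before the second evaluation. That holds only for measured change; gait speed, MoCA/MMSE and GDS have no recalled item.
- Gait tests affected by a temporary condition are to be repeated after it resolves (Tables 8 and 9). This limits short-lived slowing but not lasting loss, and it does not cover GDS or weight.
- Section 5.2.2 also plans a survival analysis, and each Clinical Frailty Index component is to be tested as a predictor (MO3). Early deaths can contribute there, but no time order is stated for that step either.
- Section 3.3 records dates of falls, fractures, hospitalisations and deaths, so the order can still be imposed at analysis.

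**Conclusion.** The point holds as a flaw in the stated analysis: the correlation allows reverse direction and gives early deaths no measured change. Before any measured change lie 57 to 59% of planned person-time for group A entry at M6, 52 to 55% for entry at M10, and about 46 to 49% counted from the first triplet. In C and D it is all of it, though those groups are 150 of 510 participants (29%) and only 750 of 11,070 person-months (7%).

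Three stronger readings are tempting and not supported. The percentages are shares of scheduled time without dropout, not shares of events. The text does not say that early deaths are discarded. Nor does it say that decline after an event will be treated as prediction; it only fails to prevent this.

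The direction of the bias follows whenever events leave a lasting loss. Its size does not follow from the documents: false significance ran from barely above 5% to over 80%, depending on the assumptions.

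**What to change.** In Section 5.2.2, replace the end-of-study correlation by a landmark analysis, or an equivalent model with time-dependent proxies:
- Relate the proxy change up to each clinical evaluation only to hard outcomes after that evaluation (A from its second evaluation; B from M16 and again from M22).
- Relate events before the second evaluation to entry values, including the past-year weight-loss and health items, so that early deaths contribute.
- Do not use C and D to validate proxy change as a predictor, since no follow-up remains after M36.
- State how ADL/IADL decline, assessed every six months, is dated relative to each landmark.
- Reconcile M26 (Section 2.5) with M27 (Section 4.2) for group A's second evaluation.

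This changes analysis wording only and needs no new data. The cost is that fewer events enter the change analysis: about 41 to 43% of planned person-time remains for it, all in groups A and B.

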3.1.5 Assessment subset 5: Balance and gait evaluation

This session consists of the evaluation of mainly three functions closely related to sarcopenia (10):

- Lower limb strength.
- Balance.
- Gait speed. More than other parameters, gait speed has shown a remarkable ability to predict survival in older adults and to reflect their general health and functional status (11).

Table 8 summarises this sub questionnaire.

Table 8. BALANCE AND GAIT EVALUATION

Lower limb strength	Raise from the chair 5 times without helping from the arms
	Number of seconds necessary to accomplish the task
	"Test non realizable" option will be provided
Balance	Single foot station
	1. <5sec
	2. >5sec)
	3. Test non realizable
Gait speed	Timed Get Up And Go Test
	Time in seconds needed to complete the task
	Speed for 4 meters' straight walk
	Time in seconds needed to complete the task
	Optional open text field will be provided in order to enter qualitative evaluation of the gait, the balance, the turn and the posture
Special conditions	Existence of a temporary condition that could affect the performance in these tests?
	1. No 2. Yes
	If yes, the evaluation should be repeated in another visit after the resolution of the condition.

During this part of the clinical assessment, movement monitoring data will also be obtained by IMUs (Inertial Measurement Units) which will be attached to the subject's upper and lower limbs since the beginning of the clinical assessment appointment. The aim of this action is to record some movement, posture and activity data from these devices during the 2 hours that lasts the appointment, also in a more standardized procedure that is the gait and balance evaluation tests. The gathering of these data will serve in the development of the WWBS (Wearable WBan System).

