Annex 10: The Geriatric Depression Scale –version 15 items

Choose the best answer for how you have felt over the past week:

1	Are you basically satisfied with your life?	Yes	0
		No	1
2	Have you dropped many of your activities and interests?	Yes	1
_		No	0
3	Do you feel that your life is empty?	Yes	1
		No	0
4	Do you often get bored?	Yes	1
		No	0
5	Are you in good spirits most of the time?	Yes	0
		No	1
6	Are you afraid that something bad is going to happen to you?	Yes	1
		No	0
7	Do you feel happy most of the time?	Yes	0
		No	1
8	Do you often feel helpless?	Yes	1
		No	0
9	Do you prefer to stay at home rather than go out and do new things?	Yes	1
		No	0
10	Do you feel you have more problems with your memory than most?	Yes	1
		No	0
11	Do you think it is wonderful to be alive now?	Yes	0
		No	1
12	Do you feel pretty worthless the way you are now?	Yes	1
		No	0
13	Do you feel full of energy?	Yes	0
		No	1
14	Do you feel that your situation is hopeless?	Yes	1
		No	0
15	Do you think that most people are better than you are?	Yes	1
		No	0

Total score:

[figure not shown]

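### The proxy-outcome curve in section 5.2.2 can never rise, so worsening depression on the GDS is fitted as steady, improving GDS as decline, and net improvement on the other scales as flat

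*Protocol*

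**What the plan says.** Section 5.2.2 lists five proxy outcomes: gait speed, MoCA and/or MMSE, GDS, weight loss and self-assessed health. The first analysis step models each one over time. The quadratic is put forward as one of several simple candidates, "such as the quadratic polynomial, for each one of the N" proxies. Its equation is f_i(t) = a − b·t − c·t², and the coefficients are described as follows: "where a, b and c positive parameters that indicate the starting point and the rate of linear and more rapid (quadratic) change, respectively".

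Three working rules come with it:

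- A curve without slope has a stated meaning: "Zero values of b and c model the steady state".
- A person seen only once or twice gets no quadratic term, so the model reduces to a straight line.
- A third visit brings the quadratic term in: "After completing three clinical evaluations, c can be also estimated".

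The second step picks out FrailSafe variables by how well they correlate with the estimated f_i.

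On scale direction, Annex 10 gives one point for each depressive answer on the GDS-15. For example, yes to "Do you feel that your situation is hopeless" scores 1, so a higher total is worse. Self-rated health in Table 14 runs from 1 (very bad) to 5 (excellent), so a higher value is better. The walk in Table 8 is recorded as "Time in seconds needed to complete the task", although the proxy is named as a speed. The protocol does not say that any proxy is reversed or rescaled before fitting.

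**The concern.** A single curve that can only fall is applied to proxies that do not all worsen in the same direction. For the GDS it reads backwards. For the higher-is-better scales it allows decline or no change but not improvement, although MO6 in Table 24 asks whether positive changes modify the expected patterns of the proxy outcomes. A one-sided restriction also biases the fit in people who are not changing: upward noise is set to zero and downward noise is kept.

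The fitted f_i are what the FrailSafe variables are correlated with, so these errors carry into variable selection. A sensor measure that tracks worsening mood would be compared with a flat line.

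**Working it through.** **Inputs.** The curve and its rules are from section 5.2.2. Group B visits are at M10, M16, M22 and M35 (section 4.3), which is t = 0, 6, 12, 25 months from entry. Group A has three visits: M6 or later, then M26 in section 2.5 or M27 in section 4.2, then M33. With M27, t = 0, 21, 27. The protocol names no fitting method and no visit-to-visit SD. I assume least squares per person with b, c ≥ 0, and SD 1.5. All score series are illustrative.

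**1. Direction.** f′(t) = −b − 2ct. With b, c ≥ 0 and t ≥ 0 this is never positive.

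**2. GDS rising evenly from 3 to 6, group B.** The values are 3, 3.72, 4.44 and 6, with mean 17.16/4 = 4.29. A flat fit is optimal when Σ(y − ȳ)t and Σ(y − ȳ)t² are both at least 0. The deviations are −1.29, −0.57, 0.15 and 1.71.

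- Σ(y − ȳ)t = 0 − 3.42 + 1.80 + 42.75 = 41.13
- Σ(y − ȳ)t² = 0 − 20.52 + 21.60 + 1068.75 = 1069.83

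Both are positive, so b = c = 0 and the fit is a constant 4.29. With noise of SD 1.5 added at each visit, simulation fits about 92% of such people as flat (91% if time is counted from entry rather than in project months). For SD 1 and SD 2 the shares are about 98% and 85%.

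**3. Other patterns, group A months 0, 21, 27.**

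| Series | Restricted fit |
|---|---|
| GDS 3, 6, 9 (worsening) | 6.00, 6.00, 6.00 |
| GDS 9, 6, 3 (improving) | 9.16, 5.59, 3.25 |
| MoCA 24, 26, 27 (improving) | 25.67, 25.67, 25.67 |
| MoCA 27, 23, 25 (partial recovery) | 26.67, 24.48, 23.85 |

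**4. False decline in a stable person, group B.** For a straight line, Σ(t − t̄)² = 342.75, so the slope SD is 1.5/√342.75 = 0.0810 per month. Keeping only the falling half gives a mean fall of 0.0810 × 0.399 × 25 = 0.81 points over 25 months. Allowing the quadratic term as well, simulation gives 0.85 to 0.88, about 0.9. The bias is proportional to the SD: about 0.6 at SD 1 (0.9 × 1/1.5) and 1.2 at SD 2 (0.9 × 2/1.5).

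**5. Three visits.** The protocol's minimum of three time points for estimating c reproduces: the design matrix for (a, b, c) has rank 2 with two visits and rank 3 with three. But 3 visits − 3 parameters = 0 residual degrees of freedom. This concerns group A, 3 × 80 = 240 people. Under the restriction, few stable people get an exact fit (about 3% have both b and c positive). Without the restriction, every three-visit fit is exact.

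**The case against.** The strongest reply is that the quadratic is introduced as one example of simple models to be investigated. Scale direction and final model form could be settled in an analysis plan that is not at hand, and raw changes in the proxies are to be assessed as well. This lowers the severity. It does not remove the error: the quadratic is the only model given, operating rules are set for it, and the sign rule carries no qualification.

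A reader might infer more than the protocol supports:

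- *That slowing gait is also missed.* The listed proxy is gait speed, which falls with worsening, so the curve fits it in the right direction. Seconds are the raw recording. The text need only state the conversion.
- *That every improvement is fitted as steady.* An improving GDS is fitted as decline, and a partial recovery on MoCA as a steady fall.
- *That group A forecasts are several times noisier than those from a straight line.* That holds for an unrestricted quadratic projected well beyond the visits. Section 5.2.2 restricts the curve, and the study ends at M36. A series that the restriction flattens is not also fitted exactly.
- *That the comparison of groups C and D is biased.* Section 2.1 frames it as evolution of frailty status measured by the frailty indices. No passage says that these curves enter it.
- *That all predictions rest on the curves.* Section 5.2.2 gives the central role to the proxy variables, and the survival step does not name f_i as its input.

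**Conclusion.** The point holds, with moderate severity. As written, the curve gives the wrong reading for the GDS in both directions, cannot show net improvement on MoCA, MMSE or self-rated health, and builds false decline into stable people. The direction result is algebraic and needs no assumption about noise. The constant 4.29 assumes least squares and an even rise from 3 to 6. The 92% and the 0.9 points over 25 months also assume a visit SD of 1.5, which the protocol does not give. The range for SD 1 to 2 is 98% to 85% and 0.6 to 1.2 points. The lack of residual degrees of freedom in group A is a separate weakness, which applies where the restriction does not bind. The practical consequence that the protocol itself supports is that FrailSafe variables are selected against distorted curves.

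**What to change.** Make three changes to section 5.2.2, together:

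1. Code every proxy in the same direction before fitting. Reverse the GDS (for example 15 − score), and state that the recorded walking seconds are converted to speed.
2. Remove the requirement that b and c be positive. Reversing the GDS alone would still leave improvement fitted as flat.
3. Do not estimate a person-specific c from only three visits; use a straight line. This has to accompany the second change, because without the restriction every three-visit quadratic fits exactly.

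A linear mixed model with random intercept and slope is one way to do this for all participants. It is an option rather than a requirement, and it shrinks individual slopes towards the mean, which matters given the stated interest in personal curves.

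As a check, the GDS series in step 2 of the working, reversed and fitted by a straight line, gives a decline of 3/25 = 0.12 points per month instead of zero. The cost is a few sentences of text and standard software. The change should be made before fitted curves are used to select FrailSafe variables.
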